4.1. Objectives

The Stroke AF study will compare the incidence rate of AF through 12 months between continuous monitoring and standard of care in subjects with a recent ischemic stroke of presumed known origin. Subjects will be randomized 1:1 to the continuous monitoring arm or control arm.

4.1.1. Primary Objective(s)

To compare the incidence rate of AF through 12 months between the continuous monitoring arm vs control arm in subjects with a recent ischemic stroke of presumed known origin.

18 December 2018 Version 4.0 Pag

Page 17 of 66 Medtronic

4.1.2. Secondary Objective(s)

To compare the incidence rates of AF through the duration of study follow-up between study arms.

5. Study Design

5.1. Study Design

Stroke AF is a prospective, multi-site, randomized, controlled, non-blinded, post-market study. The Stroke AF study will compare the incidence rate of AF through 12 months between the continuous monitoring arm and the control arm in subjects with a recent ischemic stroke of presumed known origin. Once enrolled, subjects will be randomized 1:1 (continuous monitoring vs control). Subjects randomized to the continuous monitoring arm will have a Reveal LINQ ICM inserted within 10 days of the qualifying stroke and undergo continuous remote monitoring. Subjects randomized to the control arm will be followed per site specific standard of care.

The study is expected to be conducted at approximately 40 sites located in the United States (U.S.).

It is estimated that approximately 496 subjects will be enrolled in the study. Assuming 2% attrition from enrollment to randomization, approximately 486 subjects will have randomized. A total of 23 first documented AF events within 12 months of randomization are required for the study to test the primary objective. AF will be defined as an AF event lasting more than 30 seconds and adjudicated by the endpoint adjudication committee. The analysis of the primary objective will occur after all enrolled subjects have completed 12 months of follow-up. Approximately 248 devices may be used in the study. Based on previous studies of this scope and magnitude, it is estimated that sites may identify and enroll on average one eligible subject per month.

To ensure a widespread distribution of data and minimize site bias in study results, the maximum number of subjects who may be enrolled at a single site is 50 subjects. Sites that enroll faster than others will be allowed to do so in order to maintain an adequate overall study enrollment rate. In addition, to ensure a robust dataset is available for subgroup analysis, a maximum of 50% (approximately248) subjects with lacunar stroke (i.e., small vessel disease) may be enrolled. Medtronic will notify study sites when enrollment of lacunar stroke subjects is no longer allowed, if applicable.

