The above incidence rates were used to estimate the 12 month incidence rate of AF in patients with ischemic stroke of presumed known origin. We expect the AF incidence rate to be lower in patients with an ischemic stroke of presumed known origin when compared to the incidence rate in patients with a cryptogenic stroke. Consequently, an AF incidence rate of 8% through 12 months is expected in our continuous monitoring arm. An AF incidence rate of 2% through 12 months is expected our control arm. This is the same rate observed in the control arm for the CRYSTAL AF study. Although we expect the AF incidence rate to be lower in patients with an ischemic stroke of presumed known origin, we also expect that present standard of care treatment includes more rhythm monitoring then it did during the time of the CRYSTAL AF study.

The objective of the study is to compare the incidence rate of AF through 12 months between the continuous monitoring arm vs control arm in subjects with a recent ischemic stroke of presumed known origin.

18 December 2018 Version 4.0 Page 51 of 66 Medtronic

v. Sample Size Determination

- A total of 23 events are required to demonstrate that the hazard rates are different between the two arms. Approximately 496 subjects will be enrolled. Assuming 2% attrition from enrollment to randomization, approximately 486 subjects will randomized. Subjects will be followed for 3 years, until end of device life or until official study closure, whichever occurs first. Withdrawn subjects will not be replaced.
- The assumptions used for the calculations were:
 - Two-sided log-rank test
 - Alpha = 0.05
 - 85% power
 - Annual Attrition rate = 10%
 - Annual Crossover rate = 5%
 - Follow-up Time = 1 year
 - Event-free one-year survival rate of 92% in the continuous monitoring arm
 - Event-free one-year survival rate of 98% in the control arm (hazard ratio of 4.13)

The procedure "Logrank tests (Lakatos) using proportion surviving" in PASS 2008 was used to calculate the number of events required to test this objective.

vi. Analysis Methods

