12.2. Secondary Objective

To compare the incidence rates of AF through the duration of study follow-up between study arms

i. Hypothesis

 H_0 : $h_C(t) = h_T(t)$ for t > 0 months

• H_A : $h_C(t) \neq h_T(t)$ for t > 0 months

- where $h_T(t)$ and $h_C(t)$ are the hazard functions of first detected and adjudicated AF at time t for subjects with and without the Reveal LINQ diagnostics for AF, respectively.
 - ii. Endpoint Definition

Adjudicated AF event as described in section 13.1.ii.

iii. Performance Requirements

This secondary objective will be tested in a hierarchical fashion. This means that if the primary objective is met, then this secondary objective will be tested.

The null hypothesis will be rejected if the two-sided log-rank test p-value is less than 0.05.

- iv. Sample Size Determination
- A two-sided log-rank test with the assumptions below achieves 100% power to test the secondary objective.
- The assumptions used for the calculations were:
 - Two-sided log-rank test
 - \circ Alpha = 0.05
 - Annual Attrition rate = 10%
 - Annual Crossover rate = 5%
 - Accrual Time = 2 years
 - Follow-up Time = 3 years
 - Event-free survival rate of 80% in the continuous monitoring arm
 - Event-free survival rate of 97% in the control arm (hazard ratio of 7.33)
 - Number of subjects randomized = 486

The procedure "Logrank tests (Lakatos) using proportion surviving" in PASS 2008 was used to calculate the power to test this objective.

18 December 2018 Version 4.0

Medtronic

Page 53 of 66

v. Analysis Methods

Arrhythmic episodes as described in section 13.1 will be used for this objective. However, only first detected and adjudicated AF episodes through the duration of the study follow-up will be included for analysis.

Each subject's time to first detected and adjudicated AF will be defined as in section 13.1, and Kaplan-Meier curves will be generated for each randomization arm. Subjects who have not experienced an AF endpoint through the duration of the study follow-up will be censored at their point of last contact, usable Reveal LINQ ICM interrogation or CareLink transmission, whichever is later. A two-sided log-rank test will be performed to compare the rates between arms.

In addition to the analysis on the full population, subgroup analysis for subjects with small vessel disease stroke and large vessel cervical or intracranial atherosclerosis stroke will be presented.

vi. Determination of Patients/Data for Analysis

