# 6. Determination of Sample Size

### 6.1. Primary Objective

A total of 23 first events across the two treatment groups are required to demonstrate the primary objective of the study. Assuming 2% attrition from enrollment to randomization, approximately 486 subjects will be randomized. Subjects will be followed for 3 years, until end of device life or until official study closure, whichever occurs first. However, the primary objective of the study, upon which this sample size calculation is based, will be analyzed considering data up to the 12 months follow-up visit for all subjects in the study at the time of the analysis. This sample size calculation then assumes a follow-up time equal to 1 year and an accrual time equal to zero (data from all subjects is analyzed from randomization to the 12th month follow-up visit, regardless of how long they've been in the study at the time of the analysis). Withdrawn subjects will not be replaced.

The assumptions used for the calculations were:

- Two-sided log-rank test
- Alpha = 0.05
- 85% power
- Annual Attrition rate = 10% (in each treatment group)
- Annual Crossover rate = 5% (in each treatment group)
- Follow-up Time = 1 year
- Event-free one-year survival rate of 92% in the continuous monitoring arm
- Event-free one-year survival rate of 98% in the control arm (hazard ratio of 4.13)

This document is electronically controlled. Printed copies are considered uncontrolled.

Version 2.0 15/MAY/2017

The procedure "Logrank tests (Lakatos) using proportion surviving" in PASS 2008 was used to calculate the number of events required to test this objective.

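### Does calling 23 AF events a requirement stop the primary test from being run when fewer occur?

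*Protocol*

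**What the plan says.** Four places mention 23 events.

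- Protocol 5.1 (Study Design): "A total of 23 first documented AF events within 12 months of randomization are required for the study to test the primary objective". The SAP Introduction (section 3) repeats the sentence.
- Protocol 12.1, under Sample Size Determination: "A total of 23 events are required to demonstrate that the hazard rates are different between the two arms".
- SAP 6.1, in the sample size section: "A total of 23 first events across the two treatment groups are required to demonstrate the primary objective of the study".

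The rules that govern the analysis are these.

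- **Trigger.** Two sentences after the 23-event sentence, Protocol 5.1 says: "The analysis of the primary objective will occur after all enrolled subjects have completed 12 months of follow-up". SAP 4.3 gives the detail: each subject has had the 12-month visit, has missed it and the window has closed, or has exited earlier.
- **Population.** All randomized subjects (Protocol 12.1.vii), that is, the ITT cohort (SAP 7.9, primary objective, item v).
- **Decision rule.** Reject if the two-sided log-rank p-value is below 0.05 (Protocol 12.1.iii; SAP 7.9, primary objective, item iii). No minimum count is attached.
- **Secondary objective.** It is tested hierarchically: "This means that if the primary objective is met, then this secondary objective will be tested" (Protocol 12.2.iii).

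**The concern.** A count that is required in order to test normally belongs to an event-driven trial, where enrollment or follow-up continues until the count is reached. This trial has no such mechanism. The number randomized is fixed at about 486, withdrawn subjects are not replaced, events after day 365 do not enter the primary analysis, and no interim analysis is planned. Neither document says what happens with 22 events or fewer.

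If 23 were a true gate, nearly half of the trials that run exactly to plan could not perform the primary test, and the hierarchical secondary test would be lost as well. If the sentence were simply ignored, a significant result on, say, 20 events might be attacked, or a null result excused, because the sponsor's own condition was not met. In an open-label study analyzed by the sponsor, that choice should not be left until the count is known.

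**Working it through.** **Inputs** (SAP 6.1; Protocol 12.1.v). One-year event-free proportions are 0.92 (monitoring) and 0.98 (control). Annual attrition is 10% and annual crossover 5%, each per arm. Follow-up is 1 year with zero accrual time. Randomization is 1:1, so 486 subjects give 243 per arm.

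**Step 1: hazards.** Monitoring: −ln 0.92 = 0.0834. Control: −ln 0.98 = 0.0202. The ratio is 4.13, as the plan states.

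**Step 2: where 23 comes from.** With attrition only, attrition hazard a = −ln 0.90 = 0.1054, and the one-year event probability per arm is h/(h+a) × [1 − exp(−(h+a))].

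- Monitoring: 0.0834/0.1887 × (1 − 0.92 × 0.90) = 0.4418 × 0.172 = 0.0760; × 243 = 18.5 events.
- Control: 0.0202/0.1256 × (1 − 0.98 × 0.90) = 0.1609 × 0.118 = 0.0190; × 243 = 4.6 events.
- Total: 23.08.

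With 5% two-way crossover added in a Markov model, the probabilities are 0.0746 and 0.0204, giving 18.1 + 5.0 = 23.09. Either way, 23 is the expected count at 486 randomized.

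**Step 3: chance of fewer than 23.** The count has mean 23.09 and a standard deviation of roughly √23.09 = 4.8, so 23 lies in the middle of its distribution.

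| Handling of attrition and crossover | Expected events | P(fewer than 23) |
|---|---|---|
| Attrition and two-way crossover | 23.09 | 46.2% (exact binomials); 46.5% (Poisson) |
| Attrition only | 23.08 | 46.3% |
| Attrition and one-way crossover, either direction | 23.4 to 22.7 | 43.4% to 49.2% |
| Neither | 243 × (0.08 + 0.02) = 24.3 | 36.2% |

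**Step 4: what that does to the test.** Simulated log-rank tests under attrition and two-way crossover (6,000 trials) gave:

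- power with the test run whatever the count: 0.827;
- power in trials with fewer than 23 events (45.3% of them): 0.758;
- power in trials with 23 or more: 0.884;
- probability of reaching 23 and rejecting: 0.484.

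These agree with one another: 0.453 × 0.758 + 0.547 × 0.884 = 0.343 + 0.484 = 0.827. A separate run of 20,000 trials gave 0.838 overall and 0.477 for the joint event. Enforcing a gate would therefore throw away about 0.34 of power, all of it from trials in which the test would have rejected.

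**Step 5: is there a gate?** The trigger is completion of 12-month follow-up, the population is everyone randomized, and the rejection rule is a p-value alone. SAP 6.1 also says the primary objective is analyzed on data to 12 months for all subjects. None of these depends on the count. The 0.48 figure therefore describes a procedure that the analysis sections do not specify.

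**Limit of the reproduction.** The figure of 23 reproduces as the expected count at 486, not exactly as the number needed for 85% power. For the latter, a Lakatos-type calculation gives 23.7 events without crossover and 26.2 with it; simpler formulas give 18 (Schoenfeld) and 24.1 before rounding (Freedman). The PASS settings are not given. This bears on the power claim, not on whether the test is run.

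**The case for a change.** The strongest case for a change is that the wording is plain and repeated, and that two of the four places say the events are needed to test, not merely to power the study. A plan should not give one instruction in its design summary and another in its analysis section. Neither document covers a shortfall, which is close to an even chance, and the correction would cost only a few words.

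Part of this stands. The word is wrong for a quantity that is an expectation, and the silence about a shortfall is real. The rest is weaker. The statements in Protocol 12.1.v and SAP 6.1 sit under sample size headings and report the output of a power calculation, where required is the usual term. Only Protocol 5.1 and the SAP Introduction speak of testing, and both are summaries. To treat 5.1 as a gate, one must let it override the calendar trigger in the same paragraph as well as every section that defines the analysis.

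The version history, taken only as context, points the same way: protocol version 3.0 removed an enrollment stopping rule based on AF events, and the SAP was written from version 2. That fits wording left over from an earlier scheme.

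The worry about a disputed result is also thin. A p-value below 0.05 on 20 events meets the only performance requirement stated. The secondary objective depends on the primary being met, not on a count.

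**Conclusion.** The concern does not call for a change. It is right that 23 is the expected count (23.1) described as a requirement, and that about 46% of on-plan trials would fall short (36% to 49%, depending on how attrition and crossover are applied). A chance near one half is what any design shows when its planning count equals its expected count; it is the chance of missing a number, not of failing to test or of failing to find an effect.

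The operative rules run the log-rank test at 12-month completion regardless of the count, and power at a fixed sample size already averages over the variation in events: about 0.83 overall and about 0.76 when fewer than 23 occur. Rewording the four sentences would alter no analysis, no sample size and no conclusion.

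This rests on the stated event rates, on exponential event times, on 243 subjects per arm, and on analysts following the trigger and decision rule as written. The event rates matter to the 46%, but not to the conclusion that the test is run at any count.

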5.1.1. Minimization of Bias

Selection of subjects, treatment of subjects, and evaluation of study data are potential sources of bias. Methods incorporated in the study design to minimize potential bias include (but are not limited to):

• Subjects will be screened to confirm eligibility for enrollment with defined inclusion/exclusion criteria prior to enrollment.

18 December 2018 Version 4.0 Page 18 of 66

- Subjects will be randomized 1:1 to the continuous monitoring arm vs control arm
- Demographics and medical history will be collected at baseline in order to later assess possible characteristics that may influence endpoints.
- To ensure a widespread distribution of data from study sites, no more than 10% of total expected enrollments (50 subjects) may come from a single site.
- It is recommended that all patients at an investigational site with a recent ischemic stroke of presumed known origin be screened for the study.
- All study site and Medtronic personnel will be trained using standardized training materials.
- Regular monitoring visits will be conducted to verify adherence to the Clinical Investigation Plan and source data.
- An independent clinical events committee (CEC) will be utilized to regularly review and adjudicate reported adverse events and recurrent stroke/TIAs.
- An independent committee will adjudicate AF episodes. The committee will be comprised of
 individuals experienced with identifying AF will review the device EGM records to ensure AF was
 appropriately identified.

In summary, potential sources of bias that may be encountered in this clinical study have been considered and minimized by careful study design.

5.2. Duration

The enrollment period is expected to start in early 2016 and will take approximately 42 months. Subjects will be followed for 3 years, until end of device life or until official study closure, whichever occurs first. Therefore, the expected study duration from first enrollment to official study closure (final report) is approximately 6.5 years. The duration of individual subject participation will vary based on timing of site activation and their enrollment; however, at a minimum, participation of an individual subject will be for 3 years, until end of device life or until study closure, whichever occurs first.

5.3. Rationale

The results of the Stroke AF clinical study will provide evidence that could impact the treatment and long-term prognosis for patients classified as having an IS of presumed known origin by demonstrating the value of long term monitoring for AF in this patient population. While current guidelines do recommend short term (up to 30 days) cardiac monitoring in patients after stroke, evidence generated in the Stroke AF study could influence the guidelines with regards to long term (greater than 30 day) ICM use post IS.

18 December 2018 Version 4.0 Page 19 of 66

6. Product Description

6.1. General

The Stroke AF study will be conducted using the components of the Medtronic Reveal LINQ system.

6.2. Reveal LINQ System

The Reveal LINQ system consists of 4 main components.

The Medtronic Reveal LINQ ICM is a programmable device that continuously monitors a patient's ECG and other physiological parameters. The device records cardiac information in response to automatically detected arrhythmias and patient activation.

The device is designed to record the occurrence of an arrhythmia in a patient automatically. Arrhythmias may be classified as tachyarrhythmia, brady arrhythmia, pause, atrial tachyarrhythmia, or atrial fibrillation. In addition, while experiencing or immediately after a symptomatic event, the patient can activate the device to record their cardiac rhythm.

Reveal LINQ ICM: is a small, leadless device that is inserted under the skin, in the chest. The device uses 2 electrodes on the body of the device to monitor the patient's subcutaneous ECG continuously. The device memory can store up to 27 min of ECG recordings from automatically detected arrhythmias and up to 30 min of ECG recordings from patient-activated episodes. The system provides 3 options for segmenting the patient-activated episode storage: up to four 7.5 min recordings, up to three 10 min recordings, or up to two 15 min recordings. Arrhythmia detection parameters are set to pending automatically, based on patient information entered on the programmer during pre-insertion device setup: the patient's Date of Birth and the clinician's Reason for Monitoring the patient. Arrhythmia detection parameters can also be programmed manually by the clinician.

18 December 2018 Version 4.0 Page 20 of 66

Medtronic Programmer: is used to set up the device to detect arrhythmias. It also allows the user to view, save, or print the information stored by the device.

Patient Assistant: is a hand-held, battery-operated telemetry device that enables the patient to activate the recording of cardiac information in the Reveal LINQ ICM while experiencing or immediately after a symptomatic event. The clinician uses the recorded information to determine if the symptoms were associated with a cardiac event.

MyCareLink Patient Monitor: is used by patients to gather information automatically from their inserted device and communicate the information to their physician. The inserted device communicates wirelessly with this monitor which then transmits the information over a cellular telephone connection to the Medtronic CareLink Network. This daily wireless audit transmission is scheduled by the clinic and is usually set for a time when the patient is asleep. At other times, if requested to do so by their physician or clinic, the patient can use their monitor to perform a manual device interrogation to gather information from their inserted device and communicate it to their physician. Patient interaction with their monitor includes the initial setup procedure, performing physician-requested data gathering, and responding to physician-specified notifications on the monitor screen. Refer to the literature that is included with the MyCareLink Patient Monitor for connection and usage information.

Additional information related to the Reveal LINQ ICM, including indications, contraindications, warnings and precautions can be found in the respective clinician manual.

18 December 2018 Version 4.0 Page 21 of 66

Table 1: Reveal LINQ System Component Information

Model Number	(Component (Manutacturer)	Investigational or Market- released in the United States
LNQ11 or other commercial model	Reveal LINQ Insertable Cardiac Monitor	Market- released
2090 or other commercial model	Medtronic Programmer	Market- released
960000 or other commercial model	Patient Assistant	Market- released
24950 or other commercial model	MyCareLink Patient Monitor	Market- released

6.3. Intended Population

The Reveal LINQ system is being used in accordance with the indications for the device. The Reveal ICM is indicated for:

- Individuals with clinical syndromes or situations at increased risk of cardiac arrhythmias.
- Individuals who experience transient symptoms such as dizziness, palpitation, syncope, and chest pain that may suggest a cardiac arrhythmia.

